## Other Assessments

18. Eye Tracking Task: This 15-item scale can be used to both diagnose autism and ASD, and to assess the overall severity of symptoms. The foremost criterion for the diagnosis of autism spectrum disorder (ASD) is a pervasive deficit in social communication and interaction, including abnormal speech, impaired reciprocity in relationships and conversation, and poor use and integration of nonverbal communication behaviors. A key behavior indicative of impaired social function in ASD is inappropriate or absent eye contact. For example, when gazing at faces, individuals with autism tend to direct gaze toward the mouth rather than the eyes. Changes in social communication are typically measured using multiple clinical assessments and caregiver-reported questionnaires normed for the

Full Study Title: Effect of a Wide Spectrum Nutritional Supplement on Mitochondrial Function in Children with Autism Spectrum Disorder (ASD)

Principal Investigator: [name]; Co-Investigators: [name]

Sponsor: [name]; IND 142751; ClinicalTrials.gov ID: NCT03835117; Protocol Version 02/11/2022

Funding Source: Turnabout for Autism (Private Foundation), Pleasanton CA.

ASD population. We wish strengthen measures of abnormal attention to social stimuli. We believe that objective changes in attentional gaze will be reflected in clinical presentation and overall clinician and caregiver reports of symptom severity. We may use the Tobii eye tracking software and Noldus Face Reader software to collect data about the location and duration of eye gaze while participants watch an age-appropriate video. The video will include both social and nonsocial stimuli. In each age-appropriate video, we will present a variety of simulated social interactions as well as nonsocial behaviors. We will also present speech sounds and non-speech sounds, as well as background distractors. Each of these elements will be presented across the four quadrants of the screen. We will measure the percentage of time the participant spends gazing at social stimuli and nonsocial stimuli, as well as time spent away from the screen. We will also analyze the duration of fixation for each shift in gaze. This will be performed if equipment is available and operational.

## Investigational Product

Table 2. Daily Serving Size		6.6g	8.8g	11g	13.2 g	Tolerable Upper Intake Levels
Patient Body Weight	Units	15kg-20kg	21kg-40kg	41kg-60kg	61kg-100kg	Age 4-8 years
NeuroNeeds						
Vitamin C (ascorbic acid)	Mg	450	600	750	900	ND
Vitamin D (cholecalciferol)	Mcg	11.25	15	18.75	22.5	75
Vitamin E (d- $\alpha$ -tocopheryl acetate and mixed tocopherols)	Mg	37.5	50	62.5	75	300
Thiamin (as thiamin HCl)	Mg	18.75	25	31.25	37.5	ND
Riboflavin	Mg	18.75	25	31.25	37.5	ND
Niacinamide	Mg	18.75	25	31.25	37.5	15 
Vitamin B 6 (50% as pyridoxine HCl and 50% as pyridoxal-5-phosphate)	Mg	15	20	25	30	40
(6S)-5-methyltetrahydrofolic acid	mcg	1250	1667	2084	2500	ND
Calcium folinate	mcg	1250	1667	2084	2500	400 
Vitamin B 12 (as methylcobalamin)	Mcg	375	500	625	750	ND
Biotin	Mcg	750	1000	1250	1500	ND
Pantothenic acid (as D-Ca pantothenate)	Mg	225	300	375	450	ND
Calcium	Mg	45	60	75	90	2,500
Iodine (as K iodide)	Mcg	75	100	125	150	300
Magnesium (Mg citrate and Mg malate)	Mg	150	200	250	300	110
Zinc (Zn gluconate)	Mg	9	12	15	18	12
Selenium (as selenomethionine)	Mcg	37.5	50	62.5	75	150
Manganese (as manganese amino acid chelate)	Mg	0.75	1	1.25	1.5	3
Chromium (Cr picolinate)	mcg	37.5	50	62.5	75	ND
Molybdenum (Na molybdate)	mcg	75	100	125	150	600
Potassium (K citrate)	mg	37.5	50	62.5	75	
Creatine monohydrate	mg	937.5	1250	1562.5	1875	
L-Arginine	mg	750	1000	1250	1500	
Carnitine Blend (acetyl L-carnitine HCl and L-carnitine)	mg	375	500	625	750	
Alpha ketoglutaric acid	mg	225	300	375	450	
Ubiquinone	mg	187.5	250	312.5	375	
Choline bitartrate	mg	112.5	150	187.5	225	1000
Inositol	mg	75	100	125	150	
Alpha lipoic acid	mg	75	100	125	150	
D-Beta, D-Gamma, D-Delta tocopherols	mg	3.3	4.4	5.5	6.6	300
QNeeds						
Ubiquinol (QNeeds) 	mg	200	300	400	400	

Full Study Title: Effect of a Wide Spectrum Nutritional Supplement on Mitochondrial Function in Children with Autism Spectrum Disorder (ASD)

Principal Investigator: [name]; Co-Investigators: [name]

Sponsor: [name]; IND 142751; ClinicalTrials.gov ID: NCT03835117; Protocol Version 02/11/2022

Funding Source: Turnabout for Autism (Private Foundation), Pleasanton CA.

The nutritional supplement used will be a combination of SpectrumNeeds and QNeeds, both produced by NeuroNeeds (Old Lyme, CT; See Table 1). Weight based dosing will be used. The daily serving size will be divided into two daily doses in the form of a powder which can be mixed into liquid or food. Together, there are 34 different dietary supplements in the products. Thirty-two of the 34 supplements do not exceed the Tolerable Upper Intake Limits set by the United States Institute of Medicine. The exceptions are:

1. The niacin dosing is about the upper limit. Niacin in the form of nicotinic acid is well known for causing benign flushing. Niacinamide (also known as nicotinamide) is the form of niacin in SpectrumNeeds, and this form does not cause flushing.
2. Folate exceeds the upper limit. It should be noted that half of the total folate provided is in the form of Quatrefolic™ (6S)-5-Methyltetrahydrofolic acid Glucosamine salt (55% FOLATE), which is microbial sourced, not synthetic. There is no known upper tolerable limit for non-synthetic folate, only for synthetic folate. The other half is in the form of calcium folinate. Dosage of folate used in this supplement are about one-half that commonly recommended during pregnancy to women with a prior child with a neural tube defect who may get pregnant. Dosages of folinate are one half to one-twenty-fifth the dosing commonly recommended in children with ASD. These dosages are known to be generally well tolerated in ASD children.

Except for ubiquinol, all of these nutrients are provided in a powder form in SpectrumNeeds. The physical stability and bioavailability of ubiquinol is insufficient in powder form, and thus ubiquinol is provided separately in QNeeds gel capsules. These capsules can be swallowed whole, or cut with scissors and the contents squeezed out and added to SpectrumNeeds just before ingestion.

Placebos will have the same look, feel and taste as the active treatments. For example, the SpectrumNeeds is a silica powder flavored by monk fruit extract, so the inert silica powder with the same flavoring will be used as a control. Similarly, in QNeeds, the ubiquinol is carried by purified water and glycerin colored by caramel liquid, so for the placebo the same carrier and color will be used in the gel capsule without ubiquinol.

Ongoing Examiner Reliability and Fidelity Assessments: A psychologist will train assessors at each site on the administration of the confrontational assessment. The psychologist will review the first three administrations of the language test to confirm reliable administration and conduct quarterly conference calls to review cases and to promote a common approach to conducting assessments across sites.

Data Management: Study data will be collected and managed using the REDCap software specifically developed for research and clinical trial data collection and management. REDCap is a secure web application and fully compliant with privacy guidelines and communication security as defined in the HIPAA, Federal Information Security Management Act (FISMA), and the U.S. Food and Drug CFR for electronic records.

Food and Drug Administration (FDA) Approval

The FDA has approved our Investigational New Drug (IND) application.

## 6. DATA MANAGEMENT AND STATISTICS

### Storage and Security

Study data will be managed using a 21 CFR Part 11 compliant web-based data entry system. Thus, data collection templates will be modified accordingly for data entry.

Full Study Title: Effect of a Wide Spectrum Nutritional Supplement on Mitochondrial Function in Children with Autism Spectrum Disorder (ASD)

Principal Investigator: [name]; Co-Investigators: [name]

Sponsor: [name]; IND 142751; ClinicalTrials.gov ID: NCT03835117; Protocol Version 02/11/2022

Funding Source: Turnabout for Autism (Private Foundation), Pleasanton CA.

## **Statistical Analysis**

All data analysis for the primary study aims will be conducted by the principal investigator. The primary analysis will be intent-to-treat, defined as all randomized subjects. Exploratory “per protocol” analysis will be conducted on participants who adhered to protocol. Analyses will be performed with R 3.02 (<http://www.r-project.org>) or SAS 9.3 (SAS Institute, Cary, NC).

Sample Size Justification and Power Analysis: Assuming a medium effect size of 0.5, the study provides an 80% power assuming a 0.01 alpha (allowing correction for multiple primary end-points)..

Primary Hypothesis: After 12 weeks of taking the nutritional supplement will improve mitochondrial function more than taking the placebo for 12 weeks. To test this hypothesis, we will use a mixed model using baseline and all post-randomization measures of mitochondrial activity. To deal with missing post-treatment data, the model will be conditioned on all baseline values. This conditional joint response model is more tolerant of missing data than ANCOVA and is less biased than carrying baseline data forward to endpoint.

Safety analyses: Adverse events (AE) will be systematically monitored using a 34-item form. It includes specific queries about major body systems, activity level, sleep, appetite, and general health. New events, whether presumed related to treatment or not, are classified as AEs and rated as Mild, Moderate or Severe (see details below). The occurrence of an AE will be counted once at the highest level of severity (e.g., a report of mild nausea followed by a report of moderate nausea in the same child would count as an occurrence of moderate nausea). The frequency of AEs by severity will be evaluated using a Fisher’s exact test. We will pursue exploratory analyses such as survival analyses using time to AE as the response variable.

Validation of the CGI-ASD: In addition to the standard CGI-S and CGI-I we will use a new a structured CGI rating scale called the CGI-S-ASD and CGI-I-ASD respectively. We will compare the performance of the standard and new CGI rating scales. Since the CGI-ASD provide guidance for completing the ratings we will have the rater complete the standard scale before the new scale. The correspondence between each scale and other outcome measures will be studied as well as the performance of the scales as outcome measures.

Extra Sample Collection: As an optional portion to the research, deciduous teeth and hair samples can also be collected and sent to [name] laboratory. Recent research suggests prenatal nutritional metal concentrations measured in deciduous teeth correlate with long-term language development and may predict response to various treatments and other recent studies support the measurement of unique metabolic markers using hair samples.

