Investigational Product	Weight adjusted wide-spectrum oral nutritional supplement powder and gel capsules that targets mitochondrial support produced by NeuroNeeds (Old Lyme, CT) taken in two divided doses vs oral placebos.
Safety	Physical examination, safety labs, Adverse Event Reporting, safety monitoring
Statistical Methods	The primary analysis will be intent-to-treat, defined as all randomized subjects. Mixed-model regression will determine whether blinded treatment produces a greater normalization in mitochondrial function over the 12-week period as compared to placebo treatment over the same time period. Similar analysis will test secondary outcome measures. Assuming a medium effect size of 0.5, the study provides an 80% power assuming a 0.01 alpha (allowing correction for multiple primary end-points). Secondary outcome measures will include the Improvement item of the Clinical Global Impression Scale and behavioral scales such as the Aberrant Behavior Checklist. Multivariable logistic regression will be used to select biomarkers that can significantly predict treatment response.

Full Study Title: Effect of a Wide Spectrum Nutritional Supplement on Mitochondrial Function in Children with Autism Spectrum Disorder (ASD)

Principal Investigator: [name]; Co-Investigators: [name]

Sponsor: [name]; IND 142751; ClinicalTrials.gov ID: NCT03835117; Protocol Version 02/11/2022

Funding Source: Turnabout for Autism (Private Foundation), Pleasanton CA.

Funding	Turnabout for Autism (Private Foundation), Pleasanton CA
---------	--

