The *primary aims* of this study are to evaluate the effect of a wide-spectrum nutritional supplement on mitochondrial function in individuals with ASD. Participants entered into the trial will have abnormalities in mitochondrial function that are associated with ASD (such abnormalities are found in approximately 50% of children with ASD) but are not diagnostic of mitochondrial disease. Specifically, children with mitochondrial disease (approximately 5% of the ASD population), which is a very severe disorder, will be excluded from the study so they can pursue more intensive appropriate treatment. As we believe 50% of children with ASD have some form of atypical variations in mitochondrial function, we will target these children to improve the function of their mitochondria. We hypothesizes that a nutritional supplement designed for children with ASD will have a physiological action of normalizing mitochondrial function and cellular physiology throughout the body. To test whether the targeted nutritional supplement is superior to placebo, we will study 50 children, between the ages of 2 years 6 months and 17 years 3 months, with confirmed ASD and known abnormal variations in mitochondrial at baseline. Participants will be randomly assigned to receive active treatment or placebo for 12-weeks under double-blind conditions and at the end of the 12 weeks switch to the opposite treatment arm. Mitochondrial function will be measured at baseline and after each treatment arm in order to determine if the supplement positively influences cellular biochemistry.

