#### **4. SPECIFIC AIMS**

**Primary Aim: To determine if a wide-spectrum nutritional supplement can influence**

**mitochondrial activity in 50 individuals with ASD and signs and symptoms of abnormal**

**mitochondrial function.** The trial design will be a 24-week randomized, DBPC cross-over study.

We hypothesize that the supplement will result in a greater ability to normalize mitochondrial activity as compared to placebo. To test this hypothesis we will:

- a. Test mitochondrial activity at baseline and after the placebo and supplement arms of the study and determine if the nutritional supplement normalizes mitochondrial activity significantly more than placebo.
- b. Test redox metabolism at baseline and after the placebo and supplement arms of the study and determine if the nutritional supplement improves redox metabolism significantly more than placebo.
- c. To determine if specific biomarkers (Folate Receptor Autoantibody, Single Nucleotide Polymorphism) can predict response to treatment.

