## 5. RESEARCH PLAN

### Trial Design

50 children with ASD and signs and symptoms of abnormal mitochondrial activity will be randomized in 1:1 ratio to receive a wide-spectrum nutritional supplement that targets mitochondrial function or placebo for 12 weeks under DBPC conditions. Each participant will serve as their own control in the cross-over design. Using a phone screen, we will identify children (age  $\geq$  2:6 and  $<$  17:3) with a diagnosis of ASD and evidence of mitochondrial function which is significantly higher or lower than average (here forth referred to as mitochondrial dysfunction). Children with suspicion of mitochondrial dysfunction will be invited to participate in a screening visit to make sure they meet including and exclusion criteria. If the screening visit is longer than 6 weeks from the prescreening, we will repeat the baseline metabolic testing to ensure an accurate baseline mitochondrial measurement. If they meet criteria, the baseline visit will be completed within 2 week but we will attempt to complete it on the same day (Table 1). Upon successful completion of the baseline visit, the participant will enter Phase 1 of the trial and will be randomized to receive active treatment or placebo for 12 weeks under DBPC conditions. At the end of the 12 weeks (end of Phase 1), the participant will return for evaluations similar to the ones conducted at baseline. Upon successful completion of the post-Phase 1 visit, the participant will start Phase 2 where they will receive active treatment or placebo, depending on what they received during Phase 1 – they will be crossed over to the opposite treatment regimen. Potential AEs, compliance and concomitant treatments will be monitored every four weeks.

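### The primary model is written on mitochondrial activity, but the aim is normalisation in children who may start above or below average, so it tests a net change in activity instead

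*Combined protocol and SAP*

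**What the plan says.** **The goal.** The Synopsis (Statistical Methods) states: "Mixed-model regression will determine whether blinded treatment produces a greater normalization in mitochondrial function over the 12-week period". Section 4, Primary Aim item a, is to "determine if the nutritional supplement normalizes mitochondrial activity significantly more than placebo".

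**The children.** Section 5, Trial Design, has the phone screen look for "evidence of mitochondrial function which is significantly higher or lower than average (here forth referred to as mitochondrial dysfunction", so abnormality in either direction counts. The Abstract describes participants as having "known abnormal variations in mitochondrial at baseline". Section 3 explains the interest in both directions: it cites reports of raised electron transport chain activity in some individuals with ASD.

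**The model.** Section 6, Statistical Analysis, is the only place that names the response: "we will use a mixed model using baseline and all post-randomization measures of mitochondrial activity". The hypothesis there is that the supplement "will improve mitochondrial function more than taking the placebo for 12 weeks". The model is conditioned on baseline values, a step introduced to handle missing data. Power is given as 80% for an effect size of 0.5, "assuming a 0.01 alpha (allowing correction for multiple primary end-points".

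**What is not there.** No section defines a distance from normal, a sign convention, a reference value or a treatment-by-direction term. The laboratory section says only that buccal swabs will assess mitochondrial function; it names no enzyme or index as the endpoint.

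**The concern.** When abnormality runs both ways, a change in activity and a move toward normal are different quantities. A low child who normalises goes up and a high child who normalises goes down. A treatment contrast on activity averages the two with opposite signs. Adjusting for baseline as a covariate does not prevent this: it shifts each child's expected level but leaves one common treatment effect for all.

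Two errors follow. A supplement that does what the aim hopes could be missed because its effects offset each other. A supplement that raises activity in every child could be declared successful while it pushes the high-side children further from normal. If no scale is fixed in advance, the choice between them can also be made after results are known.

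**Working it through.** **Inputs from the plan:** 50 children, each their own control in a cross-over; effect size 0.5; alpha 0.01; power 80%. **Assumptions:** two-sided test; 0.5 is the treatment difference divided by the SD of the within-child difference; complete pairs; no carry-over; a share h of children on the high side, which the documents do not give.

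**Step 1: the plan's own figure.** For a paired t-test the noncentrality is 0.5 × √50 = 3.54 with 49 degrees of freedom. Power is 0.799, so the stated 80% is reproduced. It depends on two conditions: all effects share one sign, and 0.5 is the within-child standardised difference. If 0.5 were instead a between-child standardised effect, the paired value would be 0.5/√(2(1−ρ)), and power would be 0.44, 0.58, 0.80 or 0.99 at within-child correlation ρ = 0, 0.25, 0.5 or 0.75. The plan states no correlation.

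**Step 2: every child moves 0.5 toward normal, analysed on activity.** Low children contribute +0.5 and high children −0.5.
- Net mean: 0.5(1 − 2h).
- SD of the difference: √(1 + h(1 − h)).
- Standardised effect: the first divided by the second.

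| High-side share h | Net mean | SD | Standardised effect | Power, 50 pairs | Pairs for 80% |
|---|---|---|---|---|---|
| 0% | 0.50 | 1.000 | 0.500 | 0.80 | 51 |
| 10% | 0.40 | 1.044 | 0.383 | 0.52 | 83 |
| 20% | 0.30 | 1.077 | 0.279 | 0.25 | 154 |
| 30% | 0.20 | 1.100 | 0.182 | 0.09 | 357 |
| 50% | 0.00 | 1.118 | 0.000 | 0.01 | none |

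Simulation of 100,000 trials per mix agrees to within 0.5 percentage points. At 50% the power equals alpha.

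**Step 3: the reverse case.** If activity rises by 0.5 in every child, power on activity is 0.80 at any mix. On a scale signed toward normal, the step 2 formulas apply again, giving 0.09 at 30% high-side and 0.01 at 50%.

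**Step 4: unequal effects.** If high-side children move only 0.25 toward normal, power on activity is 0.60, 0.39, 0.21 and 0.04 at 10, 20, 30 and 50% high-side, against 0.75, 0.69, 0.62 and 0.49 on the signed scale. If high-side children do not move at all, the two scales give the same power (0.68, 0.54, 0.40, 0.18) and signing gains nothing.

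**Step 5: the price of signing.** Take an all-low sample whose true levels lie a distance D below the reference, in SDs of the within-child difference, with one baseline of SD 1/√2. The chance of reading the wrong side is q = Φ(−D√2), and step 2 applies with q in place of h.
- D = 1.0: q = 0.079, net mean 0.421, SD 1.036, power 0.58.
- D = 0.5: q = 0.240, net mean 0.260, SD 1.087, power 0.17.

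Plain activity would have 0.80 in both cases.

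**The case against.** The strongest reply is that the plan leaves a metric unstated rather than choosing a wrong one. The Synopsis attaches normalisation to the mixed model itself, and the wording in the Statistical Analysis section does not rule out a derived score; the Background mentions an index of mitochondrial function in a cited study. That is fair as far as intent goes. But an aim is not a response variable, and an analyst following the one passage that names the response would fit activity and test for a net change.

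Second, the mix is unknown. The two-directional wording describes what the phone screen looks for, while the formal inclusion item asks for signs and symptoms and sets no assay direction or cut-off. A nearly all-low sample would lose little. This stands, and it is why the figures are illustrations.

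Third, a signed response can do worse than plain activity. This also stands, as step 5 shows.

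A reader might also infer that randomising without stratification on direction harms the comparison. The documents do not support that: the treatment contrast is within child, and in simulations without such stratification the signed analysis held type I error at 0.010 to 0.011 against a nominal 0.01.

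**Conclusion.** The point holds. As written, the primary model tests a net change in activity, whereas the stated aim is normalisation in a population sought in both directions. The textual gap is certain; its consequence is conditional. Under the assumptions above, power on activity falls from 0.80 with one direction only to 0.52 at 10%, 0.25 at 20% and 0.01 at 50% high-side. The stated 80% therefore applies to activity only if effects share one sign and 0.5 is the within-child standardised difference.

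A reader might go further and infer that the trial has almost no power, or that its primary analysis is bound to mislead. The documents do not support this: they give neither the high/low mix nor the effect in each direction, and the loss ranges from none to total over plausible values. Severity: should-fix.

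**What to change.** Amend the Primary Hypothesis paragraph before unblinding:

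1. Name the primary mitochondrial measure(s).
2. For each, make the primary response activity signed by the child's pre-randomisation side of the laboratory reference (+1 below, −1 above), so that positive means toward normal. Fit a mixed model with treatment, period, direction, direction-by-period and signed baseline, with child as random effect. Fix this now, with no switch of scale that depends on the data. Every randomised child receives a direction, so the intent-to-treat set stays whole.
3. Report absolute deviation from the reference as a sensitivity analysis, and plain activity with a treatment-by-direction term as supportive.
4. Restate the 80% power as applying to the named scale and the stated within-child effect size.

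The direction-by-period term is needed because signing turns a common period shift into opposite shifts for high and low children. In simulation at a 50:50 mix, power with a period term alone falls to 0.68 and 0.43 for shifts of 0.5 and 1.0; the extra term restores 0.79 and 0.78, and costs about 0.01 when there is no shift.

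**Cost.** A SAP amendment and a new power statement. No new samples are needed: Table 1 already schedules biomarker laboratories at pre-screening and at weeks 12 and 24. Signed activity does not penalise overshoot past normal and loses power when baselines lie near the reference (0.58 and 0.17 in step 5). Absolute deviation needs a reference value suited to the age range, which the documents do not give. Averaging a repeated baseline with the first could reduce misread directions, but it should be optional: Trial Design says of a late screening visit that "we will repeat the baseline metabolic testing to ensure an accurate baseline mitochondrial measurement", which may mean that the repeat is to replace the older value.

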6. **Parent Rated Autism Symptomatic Change Scale (PRASC):** The PRASC is a 12-item questionnaire that asks parent to rate changes in symptoms from “much better” to “much worse” on a 7 point Likert scale from the beginning of the intervention. This instrument was developed by [name] and Rossignol (2010) and produces a reliable measure of changes. The parent will be asked to complete this scale at each remote and onsite visit following randomization to monitor changes in ASD symptoms in the study.

Table 1. Schedule of Measures		Screening	Baseline	Double blind Phase							
Measure	Pre-Screening			*1 wk	*2 wk	*4 wk	*8 wk	12 wk	*16 wk	*20 wk	24 wk
Phase 1											
Phase 2											
Parent Ratings											
Demographics		X									
Vineland III Caregiver Form [1]			X					X			X
ABC [2]		X						X			X
PRAS-ASD [3]			X					X			X
CGSQ-Short form [4]			X					X			X
Sensory Profile 2 [5]			X								
PRASC [6]						X	X	X	X	X	X
Laboratory Assessments											
Safety Laboratory [7]	X							X			X
Biomarker Laboratories [8]	X							X			X
Pregnancy (B-HCG)	X										X
Vital Signs	X										
Height and Weight	X		X					X			X
Head Circumference	X										
Medical Assessments											
Medical/Psych History [9]		X									
Physical Exam		X									
Adverse Effects Review			X	X	X	X	X	X	X	X	X
Concomitant Treatments	X	X	X	X	X	X	X	X	X	X	X
Suicidality Assessment [10]		X	X			X	X	X	X	X	X
Compliance				X	X	X	X	X	X	X	X
Developmental Assessments											
CARS [11]		X						X			X
DAS [12]		X						X			X
OACIS [13]			X					X			X
CGI-Severity [14]			X					X			X
CGI-S-ASD			X					X			X
CGI-Improvement [15]								X			X
CGI-I ASD								X			X
Parent Target Problems [16]			X					X			X
CYBOCS-ASD [17]			X					X			X
Other Assessments											
Eye tracking task [18]			X					X			X

Full Study Title: Effect of a Wide Spectrum Nutritional Supplement on Mitochondrial Function in Children with Autism Spectrum Disorder (ASD)

Principal Investigator: [name]; Co-Investigators: [name]

Sponsor: [name]; IND 142751; ClinicalTrials.gov ID: NCT03835117; Protocol Version 02/11/2022

Funding Source: Turnabout for Autism (Private Foundation), Pleasanton CA.

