## **Laboratory Assessments**

7. **Safety laboratories**: Safety labs will be measured at the screening visit. These will include a complete blood count and a comprehensive metabolic panel.
8. **Biomarker**: Most biomarkers will be collected at baseline and after each treatment arm to determine if the treatment results in a change in these biomarkers. Baseline biomarkers will help understand whether treatment response can be predicted from biomarker tests.
  - a. Buccal swabs will be collected to assess mitochondrial function.
  - b. Plasma, Peripheral Blood Mononuclear Cells (PBMCs), DNA, and RNA will be collected and stored locally for future analysis, such as oxidative and methylation metabolism, bioenergetics, immune biomarkers, gene expression, epigenetics, and gene sequencing. 3billion Laboratory in Seoul, South Korea will perform genetic sequencing to look for causative mutations if good quality DNA is obtained and can be isolated. Samples will be stored until they are used up or destroyed, when possible. The PI, [name], will retain control over the blood sample unless it is requested that the sample be destroyed and then it will not be used for any future studies. If the participant wishes to have the sample removed from storage and destroyed at any time, they may contact a study coordinator or PI. IRB permission will be obtained prior to sharing samples for future studies. These samples will be de-identified and no protected health information will be shared with collaborators. If samples are shared, a log of those who withdraw samples will be documented thoroughly.
  - c. Deciduous teeth and hair samples will also be collected and sent to [name] laboratory. Recent research suggests prenatal nutritional metal concentrations measured in deciduous teeth correlate with long-term language development and may predict treatment response and other recent studies support the measurement of unique metabolic markers using hair samples.
  - d. Folate receptor  $\alpha$  autoantibody (FRAA) titers will be sent to the laboratory of [name], Ph.D. at the State University of New York, Downstate (Brooklyn, NY) or Iliad Neurosciences. We have demonstrated in one study that FRAA are related to methyl-B12 metabolism.

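### The therapy-stability criterion covers only 12 of the crossover's 24 weeks, and the primary mixed model does not name a period term

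*Combined protocol and SAP*

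**What the plan says.** **Design.** The Synopsis and Specific Aims describe a 24-week randomized placebo-controlled crossover with two 12-week phases. Under the Abstract, children "at the end of the 12 weeks switch to the opposite treatment arm". Trial Design adds: "Each participant will serve as their own control in the cross-over design". Phase 2 starts after the post-Phase 1 visit, and no washout is described.

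**Stability criteria (Inclusion criteria).** The educational and therapy programme must have been stable for one month, with no planned change in intensity for 12 weeks. Medication must have been stable for six weeks, with no planned change for the whole study.

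**Monitoring.** Trial Design says: "Potential AEs, compliance and concomitant treatments will be monitored every four weeks". Table 1 shows concomitant treatments at every visit.

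**Measurement.** Under Laboratory Assessments, "Most biomarkers will be collected at baseline and after each treatment arm". Table 1 places the post-randomization biomarker samples at weeks 12 and 24 only, so visit and period coincide.

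**Primary analysis (Statistical Analysis, Primary Hypothesis).** The text reads "we will use a mixed model using baseline and all post-randomization measures of mitochondrial activity". It adds that the model is conditioned on baseline values, and calls it a conditional joint response model. It lists no fixed effects, no random effects and no coefficient of interest. Specific Aims, item (a) of the primary aim, states the comparison in words: activity is tested at baseline and after each arm, to see whether the supplement normalizes it more than placebo does.

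**The concern.** In a crossover, conditions that the design relies on being steady need to be steady across both phases. Here one of two parallel criteria stops halfway. A family could plan a new or more intensive programme for week 13 and still meet the criteria. Such changes would alter the Phase 2 ratings relative to Phase 1 for reasons unrelated to the supplement.

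The standard protection against a general difference between phases is a period term in the crossover model, and the plan does not name one. If it were left out, any shift between week 12 and week 24 would go into the error term and reduce power. If the two sequences also completed Phase 2 in unequal numbers, part of the shift would leak into the treatment estimate.

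**Working it through.** **1. The two stability windows**

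| Criterion | Planned changes barred for | Share of 24 weeks |
|---|---|---|
| Medication | whole study | 24/24 = 100% |
| Education and therapy | 12 weeks | 12/24 = 50% |

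The uncovered time is 24 - 12 = 12 weeks, the whole of Phase 2, if the window is counted from the start of Phase 1. The starting point is not stated. Counted from screening, with the baseline visit up to 2 weeks later, the window could end at week 10, before the Phase 1 assessment.

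The outcomes most plausibly exposed are the behavioural ratings taken at weeks 12 and 24: CARS, CGI, ABC, CYBOCS-ASD, PRAS-ASD, caregiver strain and Vineland.

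**2. The plan's own power figure**

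Inputs from Trial Design and Statistical Analysis: N = 50, effect size 0.5, alpha 0.01, stated power 80%. Assumed, because not stated: two-sided test, paired comparison, and 0.5 measured in SDs of the within-child difference.

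- Noncentrality = 0.5 × √50 = 3.536.
- Paired t, 49 df, critical value 2.680: power 79.93%. The stated 80% is reproduced.
- With a period term, 48 df, critical value 2.682: power 79.86%. The cost is 0.07 percentage points.

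**3. If period were omitted, complete data, 25 per sequence**

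Let s be the week-24 minus week-12 shift, in SDs of the within-child difference. The supplement-minus-placebo difference has mean 0.5 - s in the supplement-first sequence and 0.5 + s in the other. The average is still 0.5, so there is no bias, but the pooled SD rises to √(1 + s²).

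| s (assumed) | √(1 + s²) | Power, period omitted (simulated) | Power, period included |
|---|---|---|---|
| 0.25 | 1.031 | about 78% | about 80% |
| 0.5 | 1.118 | 70-71% | about 80% |

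The range at s = 0.5 covers a paired analysis (70%) and a random-child mixed model with a baseline covariate (71%). A shift of 0.5 SD is as large as the whole hypothesised effect.

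**4. If completion were also unbalanced**

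Assume 40 of 50 children complete Phase 2, split 22 supplement-first and 18 placebo-first, with s = 0.5.

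- Completers only: bias = 0.5 × (18 - 22)/40 = -0.05 SD.
- Mixed model keeping all 50 (assumed correlation 0.5): bias about -0.03 SD, and 0.03/0.5 = 6% of the effect. With the split reversed, the bias is about +0.03 SD.
- Power in that mixed model is 54% (22/18) or 68% (18/22) with period omitted, against about 71% with period and sequence terms. Most of the drop from 80% to 71% comes from the lost children.
- With no true effect, 22/18 and s = 0.5, the rejection rate is 0.4% against a nominal 1%. Type I error is not inflated.

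**5. Which outcome the model should use**

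Trial Design enrols children whose mitochondrial function is well above or well below average, and the hypothesis is normalization. On raw activity, improvement is a fall in some children and a rise in others. If a 0.5 SD effect had opposite signs in the two groups, the mean effect would be 0.5 × (0.8 - 0.2) = 0.3 at an assumed 80/20 mix, 0.5 × (0.7 - 0.3) = 0.2 at 70/30, and 0 at 50/50. Power would then be no more than about 25%, 9% and 1%. Adding period to a model of raw activity would not cure this.

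**The case against.** **The contrast is not undefined.** Specific Aims item (a), the own-control statement and the biomarker schedule together state a supplement-versus-placebo comparison across both phases. The Synopsis wording, "over the 12-week period as compared to placebo treatment over the same time period", might be read as a Phase 1 comparison only, but it can equally mean equal duration. This objection stands: what is missing is the coding of treatment by phase and a named period term.

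**The plan may already allow for period.** A joint response model using every post-randomization measure would ordinarily give each visit its own mean, and here visit is period. A reader might infer that period is excluded; the text does not say so. The losses in steps 3 and 4 therefore rest on an assumed omission, an assumed shift and, in step 4, an assumed imbalance.

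**Therapy changes need not affect the primary outcome.** No passage connects therapy intensity with buccal enzyme activity. A reader might also infer a bias in favour of the supplement, but randomization spreads such changes over both sequences and they are recorded. This stands too. It limits the harm to noise and a possible period shift, chiefly in behavioural ratings, and does not explain why the two criteria differ in length.

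**Two further inferences fail.** That "All data analysis for the primary study aims will be conducted by the principal investigator" is not what leaves the model open; the silence of the text is. The direct switch at week 12 does not show carryover either: no document gives a persistence time, and Phase 2 itself puts 12 weeks between the switch and the week-24 measurement.

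**Conclusion.** The point holds as a mismatch in the eligibility criteria plus an incomplete model statement. As written, planned therapy changes are permitted for 12 of 24 weeks, while planned medication changes are barred for all 24. The expected consequence is added noise and a possible period shift, mainly in the behavioural outcomes.

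On the model, the stated power is not wrong: it reproduces at 79.93% under a two-sided paired reading. If period is in fact omitted, the cost is about 2 points of power at an assumed 0.25 SD shift and 9 to 10 points at 0.5 SD with complete data. Bias is zero under balanced completion and about 0.03 SD under the assumed 22/18 split. The documents give no shift, completion rate or within-child correlation, so these are scenarios rather than predictions. They do not support saying that the primary analysis is invalid or biased toward the supplement.

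**What to change.** 1. Reconcile the 12-week therapy-stability window with the two-phase 24-week design and with the medication criterion, and state when the window starts. This is protocol wording only. If the window is lengthened, the cost is a slightly stricter eligibility commitment for families.

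2. Write out the primary model before analysis: treatment received in each phase, period (week 12 or 24), a random child effect and baseline, with the treatment coefficient as the primary contrast. Apply it to a defined normalization outcome rather than to raw activity, since children above and below average are both enrolled. The period term costs one degree of freedom (79.93% to 79.86% power) and needs no extra children or visits.

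3. State that the period term handles shifts common to both sequences and does not remove carryover.
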